5. STUDY ASSESSMENTS AND PROCEDURES

5.1. Study Flow Chart

A detailed study flow chart (with all assessments) is displayed hereafter.

	Screening Period	Study Treatment Period						Follow-up Period
	D-30 to D-1	D0	D7	D14	D28	D56	D84	D105
		W0	W1	W2	W4	W8	W12	W15
Time Window (time between two visits ≤ 30 days)			± 2 days	± 2 days	± 2 days	± 2 days	± 2 days	± 2 days
	Screening	Baseline	V1	V2	V3	V4	V5	EOS
Obtained Informed Consent	X							
Check of IN/EX Criteria	X							
Medical History	X							
Height Measurement (cm)	X							
Body Weight (kg)	X	X	X	X	X	X	X	X
Physical Examination	X	X	X	X	X	X	X	X
Vital signs	X	X	X	X	X	X	X	X
Concomitant Medications	X	X	X	X	X	X	X	X
ECG (12 lead)	X	X					X	X*
Blood Pregnancy test (WOCBP)	X				X	X	X	X
Urine Pregnancy test (WOCBP)		X						
Randomization		X						
ABX464/placebo treatment dispensation		X			X	X		
Hematology + Biochemistry#	X#	X	X	X	X	X	X	X
Blood samples drug PK (pre-dose)				X		X		X**
Blood samples drug PK (1-, 2- & 3- hours post-dose)		X		X		X		
Blood samples for Cytokines (gel tube)		X	X	X	X	X	X	
Blood samples for Cytokines (Truculture® tube)		X				X		
Blood samples for flow cytometry cells count***		X				X		
Blood samples for CRP, ESR	X	X	X	X	X	X	X	
Blood samples for miR-124 (Paxgene® tube)		X				X		
Tender Joint Count (28)	X	X		X	X	X	X	
Swollen Joint Count (28)	X	X		X	X	X	X	
Patient Global Assessment of Disease (PtGA-VAS)	X	X		X	X	X	X	
Patient assessment of Joint Pain (Pain-VAS)		X		X	X	X	X	
Investigator Global Assessment of Disease (PrGA-VAS)		X		X	X	X	X	
Health Assessment Questionnaire – Disease Index (HAQ-DI)		X		X	X	X	X	
Functional Assessment of Chronic Illness Therapy (FACIT)-Fatigue		X		X	X	X	X	
Patient diary (dispensation/check)		X	X	X	X	X	X	
Adverse Events recording	X	X	X	X	X	X	X	X
Follow-up Headache Questionnaire in case of persistent headache (see section 5.3.2)			X (throughout the study, if needed)					
Dermatologist consultation in case of skin effect (see section 5.3.2)			X (throughout the study, if needed)					

#Tests of TB, HIV, HCV, HBV only at screening; *ECG at EOS visit in case of early termination only; **trough levels PK samples; ***Only in French Coordinating Investigator's Site; Two visits should not be conducted more than 30 days apart

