2.4. Secondary Endpoints

Main Efficacy Endpoint:

- Proportion of patients achieving a categorical ACR20 response at Week 12.

The components of ACR20 assessment include:

- C-Reactive Protein (CRP) (mg/L),
- Tender/painful joint count (TJC) (28 joints),
- Swollen joint count (SJC) (28 joints),
- Patient assessment of joint pain (Pain-VAS),
- Patient global assessment of disease (PtGA),
- Physician's Global Assessment of Disease (PrGA),
- HAQ-DI

Other secondary endpoints:

- Change from Baseline in the following disease parameters at Week 2, Week 4, Week 8 and Week 12:
 - Individual components of the ACR20 response (CRP, TJC(28), SJC(28), Pain-VAS, PtGA, PrGA, HAQ-DI)
 - Erythrocyte Sedimentation Rate (ESR);

- DAS28-CRP and DAS28-ESR. The components of DAS28 assessment include TJC(28), SJC(28), CRP/ESR, and PtGA;
- SDAI score which includes TJC(28), SJC(28), CRP, PtGA, and PrGA;
- CDAI score which includes TJC(28), SJC(28), PtGA, and PrGA;
- Functional Assessment of Chronic Illness Therapy (FACIT)-Fatigue score
- Proportion of patients achieving at Week 2, Week 4, Week 8 and Week 12:
 - ACR20/50/70 response
 - Categorical DAS28-CRP response. Proportion of patients achieving categorical DAS28-CRP response will be measured as moderate/good European League Against Rheumatism (EULAR) response at each assessment time point;
 - Low Disease Activity (LDA) ($\text{DAS28} \leq 3.2$)
 - DAS28-ESR remission ($\text{DAS28} < 2.6$)
 - ACR/EULAR remission (TJC(28), SJC(28), CRP, and PtGA: $\text{all} \leq 1$);
 - SDAI remission ($\text{SDAI} \leq 3.3$);
 - CDAI remission ($\text{CDAI} \leq 2.8$).
- Concentration of miR-124 expression in total blood (determined by qPCR) at baseline and week 8
- Change from Baseline in miR-124 expression in total blood at Week 8
- PK parameters:
 - Pre-dose plasma concentration of ABX464/N-Glu at Week 2 and Week 8;
 - Post-dose plasma concentration of ABX464/N-Glu at 1-, 2- and 3-hours post-dose at Baseline, Week 2 and Week 8;
 - Trough plasma concentration of ABX464/N-Glu at End of Study Visit
- The number of incidences of treatment-emergent serious adverse events;
- The number of incidences of treatment-emergent adverse events of special interest;
- The number of incidences of adverse events leading to investigational product discontinuation;
- The number of incidences of clinically significant laboratory abnormalities;
- The number of incidences of all AE (causally related and non-related) and SAE, further categorized by severity.

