5.2.5. End of Study Visit (Week 15 / Day 105 ± 2 days)

This EOS visit applies to all premature discontinued patients and to patients not taking part to the maintenance study. Patients will perform an End of Study Visit (EOS) three weeks after last dosing. Patients will be treated according to the standard of care since the last day of study treatment.

Following examinations/procedures should be performed:

- Physical examination and vital signs;
- Body weight;
- Hematology and Biochemistry panel;
- Blood pregnancy test for all women of childbearing potential;
- Pharmacokinetics blood samples trough levels;
- 12 leads ECG (in case of premature discontinuation only);
- Record any concomitant medications;
- Adverse Events reporting.

NB#1: In case of premature discontinuation occurring during the treatment phase (D1-D84), the above examinations should be performed as an End of Study Visit.

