7. ADVERSE EVENTS (AE) AND SERIOUS ADVERSE EVENTS (SAE)

The investigator is responsible for the detection and documentation of events meeting the criteria and definition of an AE or SAE. During the study, in case of a safety evaluation, the investigator or site staff will be responsible for reporting AEs and SAEs, as detailed in this section of the protocol.

During the screening period, only adverse event related to the screening procedures will be collected.

Any disease progression will be reported in the eCRF both as an adverse event and documented in the efficacy section.

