6.3.2 Efficacy Set with imputation (Efficacy Set 2)

Another efficacy set will use data imputation (LOCF) from Week 4.

If there are no efficacy data available, then the dropout would be considered as treatment failure.

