10 STATISTICAL METHODS

10.1 GENERAL PRINCIPLES

All statistical methods will be based on the International Conference on Harmonisation (ICH) E9 document "Statistical Principles for Clinical Trials".

Data will be summarised by treatment group. A total column showing all patients will be included for baseline and safety summaries. Where appropriate, data will also be summarised by visit with summaries for each visit attended as scheduled and an additional summary for final (last scheduled visit or early withdrawal). The format of the summaries is defined in the shells at the end of this document.

In summary and analysis tables of continuous variables, standard descriptive statistics (N, mean, standard deviation [SD], median, minimum and maximum) will be presented. Least squares mean (LS mean), standard error (SE) and 95% confidence interval (CI) will be presented in the statistical analysis outputs as appropriate. For PK summaries, arithmetic mean (AM), geometric mean (GM) and coefficient of variation (%CV) will be used to summarise the data. The minimum and maximum statistics will be presented in summary tables to the same number of significant figures as the original data. The mean/AM, median, LS mean, GM, CI, SD and SE will be presented to one more significant than the original data.

For numeric data which includes non-numeric values (e.g. PK data reported as Below Limit of Qualification (BLQ) or lab results reported as < 10 or >100) the following principles will be applied when summarising the data:

- BLQ will be replaced with a value that is ½ of the lower limit of quantification (LLQ);
- Results reported as < x will be treated in the same way as BLQ with LLQ=x;
- Otherwise AM, GM, SD, CI and %CV will not be calculated;
- Whenever meaningful, minimum, median and maximum will be presented based on the reported data (e.g. minimum = <10, median = 20, maximum = >100).

In summary tables of categorical variables, the number of non-missing observations by category will be presented with percentages. The number of missing observations will also be presented when non-zero. Unless otherwise specified, the denominator for each percentage will be the number of non-missing observations within the column. All percentages will be presented to one decimal place.

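### Early stoppers have no efficacy assessment at withdrawal, so under SAP Efficacy Set 2 a patient withdrawn for RA worsening can count at Week 12 with a score taken up to 28 days earlier

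*Protocol*

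**What the plan says.** **Assessments.** In the Protocol 5.1 flow chart, the EOS column marks weight, physical examination, vital signs, concomitant medication, pregnancy test, hematology and biochemistry, a PK trough and adverse events. The only item specific to early stoppers is the ECG: "ECG at EOS visit in case of early termination only". The rows for TJC28, SJC28, PtGA, Pain-VAS, PrGA, HAQ-DI, FACIT-Fatigue and CRP/ESR are blank at EOS. Protocol 5.2.5 gives the same list and applies it to early stoppers: "In case of premature discontinuation occurring during the treatment phase (D1-D84), the above examinations should be performed as an End of Study Visit".

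**Timing.** The same section says "Patients will perform an End of Study Visit (EOS) three weeks after last dosing" and "Patients will be treated according to the standard of care since the last day of study treatment". No separate visit at the moment of stopping is described.

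**Worsening.** Protocol 6.2 lists worsening of RA as a reason for discontinuation. Protocol 7 adds: "Any disease progression will be reported in the eCRF both as an adverse event and documented in the efficacy section". It names no measure and no visit.

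**Analysis.** Protocol 8.2 and 8.6, and SAP 3.5, count premature terminators as failures. SAP 1.2 quotes that rule under changes from protocol and says the sponsor asked for two efficacy sets. SAP 6.3.1 (Set 1) takes only patients with Week 12 efficacy data. SAP 6.3.2 (Set 2) says "Another efficacy set will use data imputation (LOCF) from Week 4", with failure only when no efficacy data exist. SAP 10.4 rules out any imputation beyond missing scale items. SAP 10.1 foresees "an additional summary for final (last scheduled visit or early withdrawal").

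**The concern.** Patients who leave because their disease worsens are not a random subset. If nothing is measured when they stop, the analysis has only the previous scheduled visit, which predates the worsening. Carrying that score forward can show such a patient at an earlier and better state. A patient who met ACR20 at Week 4 or Week 8 and was then withdrawn for worsening would count as a Week 12 responder in Set 2. Carried-forward change scores in DAS28, SDAI, CDAI and the ACR components are affected in the same way. Leaving the patient out, as Set 1 does, is also an informative loss. An analysis rule can be revised before unblinding, but an assessment that was never made cannot be recovered.

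**Working it through.** **1. What can be derived at EOS** (component lists from Protocol 5.3.7; EOS content from 5.1, 5.2.5 and Tables 1 and 2)

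| Measure | Components | Present at EOS |
|---|---|---|
| ACR20/50/70 | TJC28, SJC28, and 3 of PtGA, PrGA, pain, HAQ-DI, CRP | CRP only |
| DAS28-CRP | TJC28, SJC28, PtGA, CRP | CRP only |
| DAS28-ESR | TJC28, SJC28, PtGA, ESR | ESR unclear |
| SDAI | TJC28, SJC28, PtGA, PrGA, CRP | CRP only |
| CDAI | TJC28, SJC28, PtGA, PrGA | none |
| FACIT-Fatigue | 13 items | none |

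No composite score can be formed. The documents disagree on CRP and ESR. The dedicated flow-chart row is blank at EOS, but Table 2 includes CRP in the EOS biochemistry sample, Table 1 lists both tests in the panels, and 5.3.7 says both are measured at every visit. Table 2 has no ESR tube at EOS.

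**2. Age of the carried score.** Protocol 2.4 sets the efficacy time points ("Proportion of patients achieving at Week 2, Week 4, Week 8 and Week 12"), that is Days 14, 28, 56 and 84.

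- Nominal gaps: 28 − 14 = 14 days, 56 − 28 = 28 days, 84 − 56 = 28 days.
- With the ±2-day windows: 28 + 2 + 2 = 32 days, cut to 30 by the flow chart's cap on visit spacing.
- Examples: stopping on Day 55 uses Day 28, 55 − 28 = 27 days old. Stopping on Day 83 uses Day 56, 83 − 56 = 27 days old.

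So the score precedes withdrawal by up to 28 days (30 at the cap). This reads Set 2 as using the last visit at or after Week 4. If it means the Week 4 value itself, the gap approaches 84 − 28 = 56 days.

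**3. Weight of one patient.** Planned arms are 20 each: 1/20 = 5 percentage points.

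**4. The plan's own figure.** Inputs from Protocol 8.6: 65% vs 25%, 20 per arm, 10% two-sided. Pooled normal approximation: (0.40 − 1.645 × √(2 × 0.45 × 0.55/20)) / √((0.65 × 0.35 + 0.25 × 0.75)/20) = (0.40 − 0.2588)/0.1441 = 0.98, giving power 0.837. Exact enumeration of the likelihood-ratio test gives 0.833. The stated 84% is reproduced, and this point does not depend on it.

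**5. Illustration (assumed counts).** Suppose Set 2 shows the planned rates, 13/20 vs 5/20. With expected counts 9 and 11 in each arm, G = 2 Σ O ln(O/E) = 6.66, p = 0.010. Let k of the 13 be withdrawn patients whose carried-forward score met ACR20, and count them as failures instead:

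| k | Active arm | Difference vs 5/20 | p |
|---|---|---|---|
| 0 | 13/20 | 40 points | 0.010 |
| 1 | 12/20 | 35 points | 0.024 |
| 2 | 11/20 | 30 points | 0.051 |
| 3 | 10/20 | 25 points | 0.100 |
| 4 | 9/20 | 20 points | 0.18 |

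If the one such patient is on placebo, that arm falls to 4/20 and the difference rises to 65 − 20 = 45 points, so the shift can go either way.

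**6. Whether the failure rule removes the problem.** The SAP 14.1 list runs the efficacy tables on Set 1 and Set 2, plus one ACR20 table on the PP set. None is defined by the failure rule. That rule also supplies no value for the continuous scores.

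**The case against.** The strongest reply is that the protocol already treats premature terminators as failures, that SAP 3.5 repeats this, and that the first-named efficacy analysis (Set 1) carries nothing forward. On that view the old score comes from SAP 6.3.2, not from the flow chart, and keeping the failure rule would settle ACR20 without any new assessment. Much of this stands. The stale score arises in Set 2 only, and a reader who infers that every analysis represents early stoppers by an old score goes further than the SAP allows. But no listed table applies the failure rule, and it does nothing for the change scores.

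A reader might also infer that EOS records nothing on efficacy. That is too strong: CRP is in the EOS sample and Protocol 7 requires progression to be documented. Neither yields a composite score.

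Nor do the documents support a definite inflation of the drug effect. They give no drop-out rate, the patients concerned must have met ACR20 and then worsened before the next visit, and they could be in either arm. Where worsening is established at a scheduled efficacy visit, the full set is taken that day and the gap is zero.

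Finally, filling the EOS column would not by itself solve this. EOS falls three weeks after the last dose, on standard of care, so a value taken then could reflect other therapy.

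On importance, the primary endpoint is treatment-emergent adverse events, and the ACR20 test is interpreted descriptively.

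**Conclusion.** The concern holds in a limited form. No composite efficacy score can be derived for an early stopper after the last scheduled visit. Under Set 2, a patient withdrawn for worsening can therefore count at Week 12 with a score up to 28 days older than the withdrawal (30 at the cap). In Set 1 the patient is missing at Week 12. Each carried-forward responder is worth 5 points in a 20-patient arm. The p-values above rest on assumed counts that all fall in one active arm; they show sensitivity and are not a forecast. The plan should be changed, because ACR20 is the main efficacy endpoint and the basis of the sample size, and the change is small. The result for the primary safety endpoint is not affected.

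**What to change.** - **Assessments.** In Protocol 5.1 and 5.2.5 and SAP 16.1, add for early termination only, as is done for the ECG: TJC28, SJC28, PtGA, Pain-VAS, PrGA, HAQ-DI, FACIT-Fatigue, CRP and ESR, taken when treatment is stopped. Record days since last dose and whether RA therapy has changed.
- **Use of the value.** In SAP 6.3.2, the SAP 10.1 early-withdrawal summary and the mixed models, use it only if it was taken at stopping and before any change of RA therapy. List a value taken at the three-week EOS visit on standard of care, but do not carry it forward.
- **Responder endpoints.** In Set 2, count premature terminators as failures for ACR20 and the other responder endpoints, as Protocol 8.2 and SAP 3.5 state.
- **Consistency.** Reconcile SAP 6.3.2 with 3.5 and 10.4, and define what carrying forward from Week 4 means. Reconcile the blank CRP/ESR row at EOS with Protocol 5.3.7 and Tables 1 and 2.

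The cost is amended wording in both documents, a short set of routine assessments per early stopper, possibly an added contact at stopping, and a few off-schedule values to flag. Patients who have already stopped cannot be assessed retrospectively; for them only the analysis rules help.

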5.2. Study conduct

It is the Investigator's responsibility to ensure that all the assessments are carried out during each visit and that the intervals between visits/follow-ups are adhered to.

5.2.1. Screening Visit (within 30 days prior to Baseline/Day 0)

The patient will be informed about the general aspects of the study and will sign the informed consent form. The patient number will be allocated once the patient is created in the eCRF. Only when consent has been given may further study procedures be carried out.

During the screening phase, the following assessments will be performed:

- Signed informed consent form;
- Demographic data: year of birth and gender;

- Inclusion/exclusion criteria will be verified globally, including disease confirmation according to the revised 2010 ACR-EULAR classification criteria with at least one positive criteria among the following: Rheumatoid Factor (RF), Anti-Citrullinated Peptide Antibody (ACPA) or bone erosion;
- Body weight and height;
- Medical history;
- Physical examination and vital signs;
- 12 leads ECG;
- Hematology and Biochemistry panel;
- Blood pregnancy test for all women of childbearing potential;
- Blood samples for testing TB, HIV, HCV, and HBV;
- Blood samples for acute phase reactants;
 - C-Reactive Protein (CRP)
 - Erythrocyte Sedimentation Rate (ESR)
- Tender/painful joint count (TJC) (28);
- Swollen joint count (SJC) (28);
- Patient global assessment of disease (PtGA);
- If the patient was treated by anti- TNF α therapy, confirm the adequate wash-out of the anti-TNF α therapy has started at least and collect the reason of anti- TNF α therapy discontinuation (i.e. intolerance, primary or secondary resistance):
 - 1 month prior to screening for adalimumab and etanercept
 - 2 months prior to screening for infliximab, certolizumab pegol, golimumab
- Record all medications received within 3 months prior to baseline and note if the medication is continuing; Record all RA medication without time limitation;
- Adverse Event reporting;
- Schedule next patient visits.

NB: If patient meets all eligibility criteria, has an adequate wash-out of previous therapies and laboratory results are available, the baseline visit could be performed on the same day as screening visit. In that case, it is not necessary to repeat twice the assessments required at both visits. The following additional baseline assessments have to be performed:

- Urine Pregnancy test for all women of childbearing potential;
- Pharmacokinetics blood samples at 1h-, 2h- and 3-hours post-dose;
- Patient assessment of joint pain (Pain-VAS);
- Investigator global assessment of disease (PrGA);
- Disability index of the healthy assessment questionnaire (HAQ-DI);
- Functional Assessment of Chronic Illness Therapy (FACIT)-Fatigue
- Record any concomitant medications;
- Confirm the wash-out of the anti-TNF α therapy is complete;
- Randomization;
- Dispense study treatment to patient and instruct how to take it (first dosing at site);
- Dispense patient diary (for treatment compliance and adverse event recording) and instruct how to complete it.

5.2.2. Baseline (First dosing day / Day 0)

- Physical examination and vital signs;
- Body weight;
- 12 leads ECG;
- Hematology and Biochemistry panel;
- Urine Pregnancy (β -HCG) test for all women of childbearing potential;

- Pharmacokinetics blood samples at 1h-, 2h- and 3-hours post-dose;
- Blood samples for acute phase reactants (CRP & ESR);
- Blood (gel tubes and Truculture® tubes) samples for cytokines determination;
- Blood samples (Paxgene® tubes) for miR-124 dosage;
- Blood samples for flow cytometry cells count (including at least B & T lymphocytes, myeloid cells and macrophages) (only in the Coordinating Investigator's site);
- Tender/painful joint count (28) (TJC28);
- Swollen joint count (28) (SJC28);
- Patient global assessment of disease (PtGA);
- Patient assessment of joint pain (Pain-VAS);
- Investigator global assessment of disease (PrGA);
- Disability index of the healthy assessment questionnaire (HAQ-DI);
- Functional Assessment of Chronic Illness Therapy (FACIT)-Fatigue;
- Record any concomitant medications;
- Confirm the wash-out of the anti-TNF α therapy is complete;
- Adverse Events reporting;
- Randomization;
- Dispense study treatment to patient and instruct how to take them (first dosing at site);
- Dispense patient diary (for treatment compliance and adverse event recording) and instruct how to complete them;
- Schedule next patient visits.

5.2.3. Week 1 / Day 7 (+/- 2 days) - Visit 1

- Physical examination and vital signs;
- Body weight;
- Hematology and Biochemistry;
- Blood samples for cytokines determination
- Record any concomitant medications;
- Check treatment compliance on patient diary;
- Adverse Events reporting;
- Schedule next patient visits.

5.2.4. Week 2 / Day 14 (+/- 2 days), Week 4 / Day 28 (+/- 2 days), Week 8 / Day 56 (+/- 2 days), Week 12 / Day 84 (+/- 2 days) - Visits 2, 3, 4, 5

- Physical examination and vital signs;
- Body weight;
- 12-leads ECG (D84 only);
- Hematology and Biochemistry panel;
- Blood pregnancy test for all women of childbearing potential (except on Week 2);
- Pharmacokinetics blood samples pre-dose, 1h-, 2h- and 3-hours post-dose (Week 2 / Day 14 and Week 8 / Day 56 only);
- Blood samples for acute phase reactants (CRP, ESR);
- Blood samples (gel tubes) for cytokines determination;
- Blood samples (Truculture® tubes) for cytokines determination at Week 8 only;
- Blood samples (Paxgene® tubes) for miR-124 qPCR dosage (Week 8 only);
- Blood samples for flow cytometry cells count (including at least B & T lymphocytes, myeloid cells and macrophages) (only in the French Coordinating Investigator's site, at Week 8 only);
- Tender/painful joint count (28) (TJC28);

- Swollen joint count (28) (SJC28);
- Patient global assessment of disease (PtGA);
- Patient assessment of joint pain;
- Investigator global assessment of disease (PrGA);
- Disability index of the healthy assessment questionnaire (HAQ-DI);
- Functional Assessment of Chronic Illness Therapy (FACIT)-Fatigue;
- Record any concomitant medications;
- Check treatment compliance on patient diary;
- Adverse Events reporting;
- Study treatment dispensation on Week 4 and Week 8 visits;
- Schedule next patient visits (time between two visits should not exceed 30 days);
- On Week 12 / Day 84, enrolment of patients willing to take part to the maintenance phase.

